The initial mammography examination will be assessed by radiologists as standard of care at the Karolinska University Hospital and will be finalized prior to any selection of study persons for this study. The radiologists are therefore intrinsically blinded to whether the woman may be invited for MRI afterwards or not.

Data collection methods

Screening images including DICOM data will be transferred from the mammography equipment to a secure AI computer. On the AI computer, the images will be processed by the three component networks in the defined AI pipeline. The output will be reported in a CSV file. The CSV file will be transferred to a clinical work station where the three scores will be combined based on a predefined model and checked for being above the cut-off point for the targeted group. On the same computer, randomization of women in the targeted group will be carried out, and the patient workflow will be continuously recorded including keeping track of which women were invited, how they responded, how they were randomized and whether an MRI exam has been carried out. Data from the radiology system and the AI pipeline will be stored. Data on all cancer diagnoses will be collected through linking to the regional cancer registry and hospital records. All data will be linked based on the unique national personal identity number of each study person.

Data management

Data will remain stored at the study hospital during the course of the study. Regular backups will be performed. When required for predefined interim or final analysis, data will be extracted for research purposes under the responsibility of the PI. This data will be stored following the usual practice in the breast imaging research group at the Karolinska University Hospital, including pseudonymization before any statistical analysis. Each data parameter will undergo type and range checks for validity. Further details on data management can be found in the Data Policy document of the breast imaging research group.

Statistical methods

See separate Statistical Analysis Plan (SAP) document.

Data monitoring

There is no data monitoring committee. This has not been deemed necessary since all continuously collected data will be automatically recorded in the radiology system.

Final analysis of each outcome will take place once all relevant data has already been collected. The outcome that can be analyzed first, will be the number of cancers detected by MRI which can be carried out as soon as the last included study person has undergone MRI and that examination has been fully assessed. Analysis will be conducted under the supervision of the PI. Interim analysis will be carried out to assess any secondary outcome to the extent that it does not overlap with the primary outcome.

Harms

MRI examination confers relatively little risk. In the large Dutch DENSE study referred to above, they performed 4783 screening MRIs and encountered only 8 complications of which 5 were

categorized as serious (3 vasovagal reactions and 2 allergic reactions) and 3 less serious (2 extravasation of contrast media and 1 should dislocation).

Auditing

No auditing is planned.

Research ethics approval

See WHO above.

Protocol Amendments

Any protocol amendment will be decided by the Steering Committee. If the amendment is deemed to require additional permission by the Ethical Review Authority this will be sought before communication. Then, the amendment will be communicated to the Steering Committee and included in the updated study protocol.

Consent or ascent

Women that decide to participate in the randomization to MRI or no MRI will have signed a written informed consent. The Ethics Review Authority has waived the need for individual written informed consent from women who only undergo the regular screening mammography.

Confidentiality

All personal information will be handled according to GDPR and other applicable laws. Data will be pseudonymized before statistical analysis is performed.

Declaration of interests

The study is mainly funded by the regional authority, Region Stockholm, responsible for public health care in the area. The breast cancer patient association has also contributed funding. For activities outside this study, the principal investigator receives occasional fees for public presentations from Lunit Inc., a South Korean manufacturer of AI CAD systems for cancer detection.

Access to data

The final trial dataset will be available for the research team of the principal investigator. Pseudonymized data can be made available for external research audit. Anonymous data may be shared with academic researchers.

Ancillary and post-trial care

Not applicable. Patients are always covered by the national Swedish patient insurance.

Dissemination policy

Investigators plan to communicate findings primarily through original research papers and through participation in professional meetings. In addition, the investigators will communicate with the general public through media and through presentations at patient association gatherings. For research papers, the inclusion of co-authors will follow ICMJE recommendations. We do not intend to use professional writers outside the investigator team. While access may be granted to academic researchers, public access to complete participant-level data will not necessarily be granted. The statistical code may be shared publicly.

Appendices

None.

Approvals

ScreenTrust MRI Statisical Analysis Plan

Authors	[name], PI
Approved by	[name], study statistician
	b

STATISTICAL ANALYSIS PLAN

Revision history

Version	Date	Reason for change
1.0	March 31, 2020	
1.1	March 8 , 2023	Early stop of invitations Analysis of non-invitations

1 Preface

This Statistical Analysis Plan (SAP) describes the planned analyses for Image analysis with artificial intelligence to increase precision in breast cancer screening, the ScreenTrust MRI substudy, a prospective trial of AI triaging to invite women for supplemental screening MRI ("ScreenTrust MRI")

The trial was registered with clinicaltrials.gov (NCT NCT04832594) with an initial release date of March 31, 2021.

The planned analyses identified in this SAP will be included in future manuscripts. Exploratory analyses not necessarily identified in this SAP may be performed to support planned analyses. Any post-hoc exploratory or unplanned analyses not specified in this SAP before database lock will be identified as such in manuscripts for publication, and added as amendments to this SAP.

This SAP was written by statistician and investigator who were blinded to any assessments already performed by AI or human radiologists, and to outcomes.

2 Background

Breast cancer is the most common cancer for women. Though the patients have a relatively good probability of survival, around 1500 women die each year in Sweden from the disease. Mammographic screening has been shown to lower mortality by around 30 (1). However, in the screening programs large resources are consumed and around 30 percent of cancers go undetected and the women find them by noticing a lump in the breast (2).

MRI has consistently been shown to have a higher sensitivity than mammography, but often a lower specificity. MRI is also several times more expensive than mammography, and there is limited capacity for additional examinations in the current installations. Thus, even if MRI would increase early cancer detection, it would be offered only to a limited group of women. In a Dutch study, MRI was offered to women at average risk but extremely high mammographic density. The researchers found that the additional cancer detection rate was 16.5 per 1000 MRI screenings (compared to around 5 per 1000 mammography screenings in

the general population) (3). Since 2018 our group, together with collaborators, has developed AI-based tools that in retrospective analysis seems to offer higher precision than using mammographic density (4).

In this prospective clinical study, we will examine how using an AI pipeline to select women who are invited for MRI will affect the diagnosed breast cancers.

3 Design

This is a prospective clinical trial aiming to determine the ability of an AI pipeline to identify women who would benefit from supplemental MRI in terms of decreasing the number of cancers having a significantly delayed detection (defined in the section "4.1 Primary endpoint" below).

[figure not shown]

Figure 1. Study flow chart until Randomization.

All women attending mammography screening at Karolinska University Hospital will have their mammograms analyzed by AI (Figure 1). The specific AI-implementation (AI tool) in this study is a result of AI predictions from three equally weighted component AI models analyzing mammograms: (i) masking predictor, (ii) risk predictor and (iii) cancer signs predictor (by one commercial CAD model and one in-house academic CAD model); the age of the woman is also taken into account by multiplying the score with (110-age)/70. The purpose of the age factor is to attain a relatively similar proportion of MRI exams in the lower and higher age groups. The aim of the AI tool is to identify women with the highest probability of having a delay in cancer detection, i.e., having had a false negative screening mammogram.

The specific AI tool and its settings will remain the same during the study. For each examination, the AI tool will produce an AI Joint Score. The AI Joint Score calculation is specified in section 5.3. Women who decide to participate, will be randomized to MRI or no-MRI (standard-of-care).

A Signa Premier 3T MRI scanner from GE Healthcare will be used. The MRI protocol will contain a T2-weighted Dixon sequence and a T1-weighted dynamic contrast enhanced series, and will remain the same through the course of the study. All MRI exams will be assessed by two radiologists, where the second reader will have access to the assessment of the first reader. In case of disagreement, a consensus discussion between two radiologists will be held. The MRI exams will be assessed according to BI-RADS, and follow-up will depend on the BI-RADS category (Figure 2). Women with BI-RADS 1-2 will have no further diagnostics and will be sent a 'healthy letter'. Women with BI-RADS 3 to 5 will be recalled for 2nd look ultrasound. Women with BI-RADS 4-5 will be included in the regular process for established cancer suspicion and be discussed in a multidisciplinary team conference. For women with BI-RADS 3, the follow-up will be handled within the breast radiology unit.

[figure not shown]

Figure 2. Workflow for patients invited for MRI.

3.1 Study population

The study will include healthy women attending regular mammographic screening program at Karolinska University hospital in Stockholm. All consecutive women will be included; the ethical review authority waived the need for individual informed consent at this stage.

- Inclusion criterion
 - Women in the population-based screening program for whom a standard fourview mammography examination was acquired (right MLO, right CC, left MLO, left CC)
- Exclusion criteria
 - o Women in surveillance program referred from the hereditary cancer unit
 - Breast implants
 - \circ $\;$ Women in surveillance program due to prior breast cancer $\;$
 - Breast feeding
 - MRI contraindication requiring radiologist assessment

3.2 Study period

The study started on April 1, 2021. Invitations will not be sent after May 2023. The inclusion may be paused during general holidays, due to staffing difficulties, specifically the summer holiday which encompasses around 2 months from second half of June to second half of August.

AMENDMENT IN MARCH 2023 (replacing any conflicting statements compared to the above):

The last participant invitations will be sent out in May 2023. The reason is that some women included in April 2021 will return for their next screening, and we wish to avoid the inconsistency that some women would have two screening rounds included while others would have only one round. This will likely lead to that we have performed less than the 1,000 MRI exams that we aimed for. An assessment of MRIs revealed a higher cancer detection rate than we had anticipated, which should results in a bigger effect size than we had assumed in our sample size calculations for the study. Thus, we believe that the statistical power in the trial will be similar to what we had originally anticipated, even with the smaller number of participants. See also the section about sample size calculations (Section 5.7).

4 Objectives and Endpoints

The purpose of the study is to examine AI-based triaging of a small proportion of women with the objective to reduce the number of significantly delayed cancer diagnoses through the use of supplemental screening MRI.

4.1 Primary endpoint

Our study has a primary composite endpoint (CEP) representing **significantly delayed cancer detection** – having any of the below characteristics:

- Interval Cancer
- Cancer with lymph node metastasis
- Cancer with invasive component larger than 15 mm

4.2 Secondary endpoints

To the extent that a secondary outcome measure does not overlap with the primary outcome, it may be included in interim reporting.

4.2.1. Number and age of women eligible and not eligible for MRI, women invited, women declined and women accepted to participate; including reason for non-participation (contraindication, patient choice, no response).

4.2.2. Distribution of AI scores for: i) Joint model, ii) AI risk score, iii) AI masking score, iv) AI CAD score(s).

4.2.3. a) Breast cancer diagnosed by screening MRI.

b) All breast cancers diagnosed during the study time including the initial screening, including mode of detection (MRI, mammographic detection, clinical detection including time since screening) for all women for whom AI scores were calculated (above and below threshold)

For all cancers in the outcome measures, the following tumor characteristics will be reported:

a) Invasiveness (in situ or invasive; micro-invasive counted as in situ)

b) Histology (ductal, lobular, mucinous, tubular, other)

c) Lymph node status (0, 1-3, or more than 4 lymph node metastases)

d) Tumor size (in mm) – in situ and invasive component separately measured by pathologist

e) Ki-67 percent. With a 20% binary cut-off, and an ex 14% cut-off level

d) Molecular subtype (Luminal A-like defined as estrogen and/or progesterone receptor positive and HER2 negative and KI-67 <14%, Luminal B-like defined as estrogen and/or progesterone receptor positive and HER2 positive/negative and KI-67 >=14%, HER2-positive defined as estrogen and progesterone receptor negative and HER2 positive, and Triple negative defined as estrogen and progesterone receptor and HER2 negative)

4.2.4. Radiological process measures: distribution of BI-RADS scores (amount of fibroglandular tissue, background parenchymal enhancement, and any lesion); number and outcome of second look ultrasound, biopsies, short-term MRI follow-up. We will report operational characteristics of the screening MRI (cancer detection rate, recall rate, positive predictive value for 2nd look ultrasound decision and for biopsy decision).

4.2.5. Questionnaire for women undergoing MRI: self-examination habit (yes, sometimes, often); previous MRI (yes, no); prior breast cancer (yes, no, which breast and year); prior nonmalignant breast disease (yes, no, which year); first-degree relative with breast cancer (yes, no, at what earliest age); first-degree relative with ovarian cancer (yes, no, earliest age); Age of menarche, Parity, Age of first pregnancy, Number of children born, Time of breast-feeding, date of latest menstruation; reason for no menstruation, use of hormonal medications; use of Cozaar or Losartan; Current length and weight. They may also fill in a questionnaire concerning their experience of undergoing a screening MRI.

4.3 Exploratory objectives and endpoints

The first exploratory objective is to examine the MRI cancer detection rate if having the cutoff point at each percentile above the actual cut-off point (e.g., at the 95th, 96th, 97th, 98th, 99th percentile).

The second exploratory objective is to determine the overall cancer detection rate for each cut-off points at each percentile of the AI score (1st, 2nd, 3rd,...,98th, 99th).

The third exploratory objective is to examine the effect of each of the three AI networks in the pipeline by one-at-a-time setting the AI score equal to the population average, and for each of these three set-ups re-analyze the overall cancer detection rate according to the above second exploratory objective.

The fourth exploratory objective is to examine the influence on cancer incidence and detection of the following potential predictors or modifiers will be explored (further detailed in the Statistical Analysis Plan): Radiologist assessments of screening mammogram at inclusion, Age, Density, AI scores: Overall pipeline (the basis for cut-off point), and various cut-off points for each of the three AI components (risk, masking and CAD).

The fifth exploratory objective is to conduct a reader study to understand if the mammograms of the women selected by the AI pipeline and in which MRI detected cancer, could represent a screening radiologist mistake. This will be examined by performing a blinded review of the mammograms of women with MRI-detected cancer mixed with mammograms of other women and a random selection of mammograms in the invited group who did not have MRI-detected cancer.

The sixth exploratory objective is to conduct a hypothesis-generating reader review of the MRI examination for women who had MRI but nevertheless were diagnosed with interval cancer or screen-detected cancer at the following screening

The seventh exploratory objective is to conduct a hypothesis-generating reader review of the women who were assigned a BI-RADS 3 category at MRI, in order to understand who the number of women in this category could be minimized

5 Statistical methods

The methods and statistical analysis used in the study is described here. Analysis of the primary endpoint will take place only after the follow-up period has passed for all study persons; there will be no public interim analysis. However, there may be a statistical analysis during the second year of the study to ascertain that the study is likely to reach the predefined statistical power. For secondary endpoints there may be interim analyses, to the extent that these do not overlap with the analysis of the primary endpoint.

All statistics will be performed using Stata version ≥ 16 or R version ≥ 4.0 .

5.1 Populations

The study population consists of all consecutive women attending regular screening mammography at Karolinska University Hospital in Stockholm having a normal assessment (i.e., not being recalled for further assessment by the consensus discussion). The prior data for each woman consists of: mammographic images, date of examination, age at examination, assessment by first radiologist, assessment by second radiologist, decision by consensus discussion (if any), AI scores from the three component models and a summary score, pathology-verified cancer diagnosis (if any) including key cancer characteristics (listed in section 4.2).

5.2 Demographics and baseline data

All data will be presented using descriptive statistics. Continuous variables will be summarized using number of women, mean, standard deviation, median, interquartile range (IQR), minimum and maximum. Categorical variables will be categorized as described in the end-points and summarized using the number and percentage of cases in each category.

5.3 Setting the operating point of the AI system

The AI tool will be calibrated based on a reference population of all consecutive screening mammograms collected during March 1 to March 17, 2021. From the distribution of the output of each AI model, the reference mean and reference standard deviation will be calculated and used to define the parameters for standardization of the scores from each component network (standardized value = (score - reference mean) / reference standard deviation). The joint score will be calculated by equal weighting of AI scores from the three components (risk prediction, masking potential, cancer detector). For the cancer detector, there will be two models used, each contributing equally. All model parameters will be fixed before study start and remain the same throughout the study. Finally, the joint score will be weighted to reflect remaining life years by multiplication with: (110 years - current age)/70. The purpose of the age factor is to achieve an approximately even distribution of MRI across the youngest and oldest age groups. The AI Masking Score cut-off point was defined by the median of examinations collected during the initial period of March 1 to March 24, 2021. The AI Joint Score cut-off point was defined to have 8% of the initial population in the eligible group to be invited. The reason behind selecting approximately 8% is that it roughly corresponds to the proportion of women having the highest BI-RADS density score of extremely dense breast. Another reason is that the selected population should contain a relatively high concentration of our composite endpoint of cancer of significantly delayed detection (i.e., around 14 per 1000 women).

5.4 Primary analyses: Superiority

Superiority analyses in terms of the absolute incidence of the primary CEP (significantly delayed cancer detection) further defined in the primary end-point (4.1). The study has been powered for the primary analysis of difference in CEP between the MRI and the no-MRI (standard of care) arms of the study.

Analyses will compare the difference CEP between study arms. This can be done on an absolute or a relative scale. The primary analysis will be performed on an absolute scale and supportive analyses may use a relative scale.

Absolute scale. The absolute difference in CEP is defined as the CEP the standard arm minus the CEP in the experimental arm (Δ CEP = CEP_{Std}- CEP_{Exp}) or vice versa, as appropriate. It is estimated by plugging into the formula the observed proportions. An approximate 100(1-a)% two-sided Wald confidence interval for Δ CEP is calculated as

$$\widehat{\Delta CEP} \pm z_{\alpha/2} \sqrt{\frac{\widehat{CEP}_{Exp} * (1 - \widehat{CEP}_{Exp})}{n_{Exp}} + \frac{\widehat{CEP}_{Std} * (1 - \widehat{CEP}_{Std})}{n_{Std}}}.$$

Relative scale. The relative difference in CEP is defined as the CEP in the experimental arm divided by the CEP in the standard arm (rCEP = CEP_{Exp}/CEP_{Std}) or vice versa, as appropriate.

It is estimated by plugging into the formula the observed proportions. An approximate 100(1-a)% two-sided Wald confidence interval for rCEP is calculated as

$$exp\left(log(r\widehat{CEP}) \pm z_{\alpha/2}\sqrt{\frac{1}{\widehat{CEP}_{Exp}*n_{Exp}} - \frac{1}{n_{Exp}} + \frac{1}{\widehat{CEP}_{Std}*n_{Std}} - \frac{1}{n_{Std}}}\right)$$

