The study shall enroll study persons until 1000 women have undergone MRI scanning. With an 95% attendance rate after invitation to MRI, we estimate that around 1050 women have been invited for MRI (and thus included in the MRI group). Given the variable randomization ratio, described above, we estimate that a slightly larger number of women have been included in the non-MRI group.

AMENDMENT IN MARCH 2023: Due to a decision to cease to invite women after May 2023, the sample size of 1000 performed MRI exams will not be attainable. An assessment of MRIs revealed a

higher cancer detection rate than we had anticipated, which should results in a bigger effect size than we had assumed in our sample size calculations for the study. Thus, we believe that the statistical power in the trial will be similar to what we had originally anticipated, even with the smaller number of participants. See also "completion date" below as well as the section about sample size calculations in the SAP.

Recruitment Status

Active

Primary Outcome(s)

The primary outcome is a composite endpoint representing **early detection failure** – a breast cancer diagnosed with any of the below characteristics:

- Interval cancer
- Cancer with invasive component larger than 15 mm
- Cancer with lymph node metastasis

The follow-up time starts once the initial mammography and screening MRI are fully processed and any cancer detected at the initial examination has been diagnosed. Thus, the cancers that will be considered for primary outcome are the women that are healthy after the initial examination. A positive primary outcome will be based on interval cancers and the cancers that are screen-detected during a 27-month follow-up time after initial screening and fulfil the above criteria.

Secondary Outcome(s)

To the extent that a secondary outcome measure does not overlap with the primary outcome, it may be included in interim reporting.

1. Women invited, women declined and women accepted to participate; including reason for non-participation (contraindication, patient choice, no response).

2. Distribution of AI scores for: i) Joint model, ii) AI risk score, iii) AI masking score, iv) AI CAD score(s).

3. a) Breast cancer diagnosed by screening MRI.

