5.7 Sample size

The sample size calculation relates to the primary analysis after women have undergone the baseline mammogram. We have estimated that the study would have a at least 90% power in detection of a statistically significant (p<0.05) difference in the absolute incidence of the primary endpoint of significantly delayed cancer (defined in 4.1), under the following assumptions:

- 50% of the women invited will agree to participate (not relevant)
- 84% of the significantly delayed cancers are averted by undergoing MRI (based on DENSE trial)

- 80% of the women will participate in the subsequent screening (around two years after the initial screening)
- 28.6 (approximately twice as many cancers detected as we assumed before study start) per 1000 women having a significantly delayed detection in the population selected by the AI tool
- The randomization rate will be around 1:1 for MRI vs. no-MRI (standard of care)

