5.8 Adjustment for multiplicity

We will not perform any correction for multiple comparisons. Each analysis will be presented with unadjusted 95% confidence interval.

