5.9 Handling of missing data

Endpoints

Our primary approach is of intention-to-treat-type (defined by which arm they are randomized to, MRI or not MRI); for any examination where the I process failed, study inclusion is not possible. In addition, we will perform a per-protocol analysis (defined by whether they underwent MRI or not).

Patient characteristics

Since data collection is performed through the electronic medical record, missing data is expected to be minimal. For analyses where patient characteristics are used (e.g., analyzing the interaction between a patient characteristics and study outcomes), we will exclude patients with missing data. As a sensitivity analysis, we will impute the missing data using the mean or median, whichever is appropriate.

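### SAP 5.4 offers only Wald intervals for about 3 to 6 expected MRI-arm events: the optional ratio interval needs a zero-event rule, and the primary difference interval is sound but slightly lopsided

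*Combined protocol and SAP*

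**What the plan says.** SAP 5.4 sets the hierarchy: "The primary analysis will be performed on an absolute scale and supportive analyses may use a relative scale". For each scale it prints one formula, introduced with "An approximate 100(1-a)% two-sided Wald confidence interval for" the quantity concerned. The difference formula uses the unpooled variance. The ratio formula contains the log of the observed ratio and, in its variance, the reciprocal of the MRI-arm event count. Either quantity may be turned round. The SAP names no score, exact or corrected method and gives no rule for an arm without events.

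SAP 5.8 adds: "Each analysis will be presented with unadjusted 95% confidence interval". SAP 5.9 makes intention to treat primary and then says "we will perform a per-protocol analysis (defined by whether they underwent MRI or not").

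The inputs that fix the expected number of events are in SAP 5.7 and in the protocol's Sample Size section. They are a composite rate of 28.6 per 1000 in the selected women, "84% of the significantly delayed cancers are averted by undergoing MRI", 80% participation in the next screening round, "The randomization rate will be around 1:1 for MRI vs. no-MRI (standard of care"), and, in the protocol, "With an 95% attendance rate after invitation to MRI".

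**The concern.** A Wald interval relies on a normal approximation that weakens when one arm has only a few events. The effect assumed here leaves few events in the MRI arm.

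The two scales are affected differently. The ratio formula stops working with zero MRI-arm events, which is the result most favourable to MRI. Any substitute would then be chosen with the data in view. The difference formula still returns an interval, but the MRI arm then adds nothing to its variance, and with small counts the interval sits off-centre. What is at stake is how the size of the benefit is reported, not whether superiority is declared.

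**Working it through.** **Inputs.** Control rate 0.0286 and 84% averted (SAP 5.7); 95% MRI attendance (protocol, Sample Size); intention to treat (SAP 5.9); about 1:1 allocation (SAP 5.7). The number analysed after the early stop is not stated, so 500 to 1000 per arm is an assumption. SAP 5.7 does not say how the 80% participation figure enters, so results are shown without it and with it multiplying both rates.

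**The plan's own figure.** SAP 5.7 claims "at least 90% power in detection of a statistically significant (p<0.05) difference in the absolute incidence of the primary endpoint" but gives no sample size beside it, so there is no single value to reproduce. Exact power of the Wald rule without the 80% factor is 82.9% (500 per arm), 89.7% (600), 93.9% (700) and 98.8% (1000), reaching 90% at about 610. With the factor it is 72.4% (500), 87.3% (700) and 91.6% (800). The claim is therefore attainable within the assumed range.

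**MRI-arm rates.**
- Intention to treat: 0.0286 × (1 − 0.84 × 0.95) = 0.0286 × 0.202 = 0.00578.
- With the 80% factor: 0.00578 × 0.8 = 0.00462.
- Women who underwent MRI: 0.0286 × (1 − 0.84) = 0.0286 × 0.16 = 0.00458.

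**Expected events and chance of none.** Expected events = n × p; P(0) = (1 − p)^n. The per-protocol column uses n = 0.95 × arm size.

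| Per arm | Expected, ITT | P(0), ITT | Expected, ITT with 80% | P(0), ITT with 80% | P(0), per protocol |
|---|---|---|---|---|---|
| 500 | 2.9 | 5.5% | 2.3 | 9.9% | 11.3% |
| 600 | 3.5 | 3.1% | 2.8 | 6.2% | 7.3% |
| 700 | 4.0 | 1.7% | 3.2 | 3.9% | 4.7% |
| 1000 | 5.8 | 0.3% | 4.6 | 1.0% | 1.3% |

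At zero events the ratio formula needs log(0) and 1/0. Inverting the ratio puts zero in its denominator and leaves the same infinite variance term.

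**Difference interval.** These results sum over all pairs of binomial outcomes, for equal arms of 500 to 1000 in steps of 100. Each tail is nominally 2.5%.

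| Method | Coverage | Upper limit too low | Lower limit too high |
|---|---|---|---|
| Wald | 94.6–94.8% | 3.6–4.0% | 1.4–1.7% |
| Wald, 80% factor | 94.0–94.9% | 3.5–4.5% | 1.2–1.6% |
| Miettinen-Nurminen | 94.9–95.1% | 2.0–2.2% | 2.7–3.0% |

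With 28.6 per 1000 in both arms, the Wald rule has two-sided type I error of 5.0–5.1% over 500:500 to 1000:1050. Its one-sided error favouring MRI is 2.5–2.7%.

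**Two worked results, per 1000.**
- 4/600 against 17/600: difference 21.7. Standard error = √(0.00667 × 0.99333/600 + 0.02833 × 0.97167/600) = 7.54. Wald 21.7 ± 1.96 × 7.54 = 6.9 to 36.5; Miettinen-Nurminen 7.5 to 39.0.
- 0/600 against 17/600: difference 28.3. The MRI-arm variance term is 0, so the standard error is 6.77. Wald 15.1 to 41.6; Miettinen-Nurminen 17.8 to 44.9. The Wald ratio interval does not exist; the score ratio interval is 0 to 0.22.

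**Sensitivity.** The protocol's background gives a fall in interval cancers from 5.0 to 0.8 per 1000, which is 4.2/5.0 = 84%. It also gives a fall in node positivity from 45% to 15%, which is 30/45 = 67%. If MRI averts only 60–67% of the composite (an assumption), 5 to 12 MRI-arm events are expected, zero events have probability of at most about 0.5%, and Wald coverage is about 94.8%. In the other direction, at half the current control rate (14.3 per 1000, close to the figure of around 14 in SAP 5.3), zero events have probability 23.5% at 500 per arm and 13.2% at 700.

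**The case against.** The strongest reply is that nothing decisive rests on this. The ratio is optional, and SAP 5.8 governs analyses that are presented, so it does not oblige anyone to present a ratio. With zero MRI-arm events the primary difference is still computable and clear of zero. The SAP Preface also says that analyses not specified before database lock will be labelled as such and added by amendment, so a late substitute would be visible. All of this stands. Labelling is disclosure rather than prespecification, though, and a formula printed in the plan should work under the plan's own assumptions.

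On the primary interval, the reply is that Wald errs on the cautious side. The limit nearer zero guards against overstating benefit. Wald misses there in 1.4–1.7% of trials, within the nominal 2.5%, while the score interval misses in 2.7–3.0%. This also stands, and it is why changing the difference interval is a preference rather than a correction.

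A reader might infer something stronger: that few events make the primary superiority analysis invalid or inflate its false-positive rate. The documents do not support that. On their inputs coverage is close to 95%, type I error is about 5%, and power is the same as with the score method in equal arms.

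**Conclusion.** The point holds as a minor, inexpensive improvement. The ratio interval in SAP 5.4 has no value when the MRI arm has no events. Under intention to treat the chance of that runs from 5.5% (500 per arm) to 0.3% (1000), or from 9.9% to 1.0% if the 80% figure scales the rates, and it is higher per protocol.

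The primary Wald difference interval is acceptable. Its one blemish is uneven misses, which slightly understate how large the benefit could be.

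These sizes depend on the assumed 500 to 1000 per arm, on 84% averted applying to the whole composite, on 95% attendance, and on how the 80% figure is meant to enter. If MRI averts about two thirds of the composite or less, the ratio problem nearly disappears. The absence of a zero-event rule depends on none of these assumptions.

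**What to change.** Add to SAP 5.4, before the primary analysis: *Any risk ratio, by intention to treat or per protocol, will be reported with a 95% score interval; if one arm has no events, only the informative limit will be given.* Preferably also: *The risk difference will be reported with a 95% Miettinen-Nurminen interval and tested with the matching two-sided 5% score test.* State in 5.9 that the same methods apply to the per-protocol analysis.

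The cost is wording only. Power is unchanged for equal arms of 500 to 1000. It is up to about 0.7 points lower if the no-MRI arm is 5–10% larger; for example, at 600:660 it goes from 91.7% to 91.1%. The score difference interval misses in about 3% of trials on the side that overstates benefit. If the sponsor prefers to keep Wald for the difference, the zero-event rule for the ratio is the minimum to add.
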